2.4.2.3 Inclusion Criteria

- (1) Female patients who underwent gynecologic laparoscopic total hysterectomy under general anesthesia;
- (2) Age between 18 and 65 years;
- (3) Surgical duration ranging from 0.5 to 4.5 hours;
- (4) Anesthesia duration ranging from 1 to 5 hours;
- (5) Willingness to receive acupuncture therapy without a history of adverse reactions such as needle syncope;
- (6) Provision of signed informed consent.

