2.4.4 Sample Size

This study was designed as a randomized controlled trial, with the treatment group receiving abdominal acupuncture and the control group receiving conventional therapy. The primary outcome measure was the time to first postoperative flatus. Based on published literature, the mean \pm standard deviation of the time to first flatus in the control group was 37.60 ± 4.11

hours. It was anticipated that abdominal acupuncture would reduce this time by approximately

8.1 hours. Assuming a two-sided $\alpha = 0.05$ and a statistical power of 90%, the sample size was

$$n = \frac{2(z_\alpha + z_\beta)^2 * \sigma^2}{\delta^2}$$

calculated using the standard formula:

The required sample size was determined to be 33 participants per group. With a 1:1 randomization ratio, both the abdominal acupuncture group and the control group required 33 participants each. Allowing for a potential 15% dropout or loss to follow-up, the minimum enrollment target was set at 38 participants per group, resulting in a total sample size of no fewer than 76 participants.

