4.1 General Parameters

Collected variables included age, body mass index (BMI), intraoperative blood loss, operative duration, and length of postoperative hospitalization.

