4.3.3 Relevant Assessment Scales

- **Pain assessment:** The Visual analogue scale (VAS) was applied (Appendix 1). Abdominal pain scores were recorded before and after treatment on the day of surgery (5 days after surgery).
- **Gastrointestinal symptom assessment:** Symptom scoring was based on the Perioperative Clinical Evaluation Standards for Gastrointestinal Motility (Guangdong Provincial Standard, Appendix 2). Scores were documented daily from the day of surgery (before treatment) through postoperative Days 1–5, according to observed gastrointestinal function.
- **Quality of life assessment:** The Gastrointestinal Quality of Life Index (GIQLI) was employed (Appendix 3). Assessments were performed on the day of surgery prior to treatment, on postoperative Day 5, and again on Day 14 following the final treatment session.

5. Adverse Events and Management

If adverse reactions occurred during the trial—such as needle stagnation, syncope, breakage, hematoma, or infection—investigators promptly managed the event, ensured patient safety, reassured the participant with an explanation, and documented the details in the case report form.

6. Ethical Principle

This clinical trial was reviewed and approved by the Ethics Committee of Guangdong Provincial Hospital of Traditional Chinese Medicine prior to participant enrollment (Approval No. YF-2023-435-01). The study was conducted in full compliance with the principles of the Declaration of Helsinki.

7. Statistical Analysis

Data were organized and managed using Microsoft Excel to establish a primary database, which was subsequently converted into an SPSS 26.0 database for statistical analysis. The Shapiro–Wilk test was employed to assess the normality of continuous variables. According to data distribution, descriptive statistics were presented as mean \pm standard deviation (SD) for normally distributed variables, and as median with interquartile range [P₂₅, P₇₅] for non-normally distributed variables. Between-group comparisons of normally distributed data were performed using independent-samples t tests, while within-group pre- and post-treatment comparisons were conducted using paired t tests. For non-normally distributed data, the Mann–Whitney U test was applied for between-group comparisons, and the Wilcoxon signed-rank test for within-group comparisons.

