Categorical variables were expressed as frequencies (n) and percentages (%), with between-group comparisons analyzed using the chi-square test or Fisher's exact test, as appropriate. Repeated measures analysis of variance (ANOVA) was applied for comparisons across multiple time points between groups. All statistical analyses were two-tailed, and a P value of less than 0.05 was considered statistically significant.

8. References

2. Boeckxstaens GE, de Jonge WJ. Neuroimmune mechanisms in postoperative ileus. *Gut*. 2009;58(9):1300-1311. doi:10.1136/gut.2008.169250
4. Mythen MGM. Postoperative gastrointestinal tract dysfunction: an overview of causes and management strategies. *Cleve Clin J Med*. 2009;76 Suppl 4:S66-71. doi:10.3949/ccjm.76.s4.11
5. Kehlet H. Surgical Stress Response: Does Endoscopic Surgery Confer an Advantage? *World J Surg*. 1999;23(8):801-807. doi:10.1007/s002689900583

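### The primary comparison of time to first flatus is fixed as an unadjusted two-sample test, giving up whatever precision the already collected age, BMI and operative duration could add

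*Protocol*

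**What the plan says.** Section 2.4.4 of the protocol names the endpoint: "The primary outcome measure was the time to first postoperative flatus". Section 7 chooses the test by a normality check. For normal data, "Between-group comparisons of normally distributed data were performed using independent-samples t tests"; otherwise the Mann-Whitney U test is used. The repeated-measures ANOVA in the same section is for outcomes seen at several time points and does not apply to a single time per patient. No covariate-adjusted model is described.

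Section 4.1 states: "Collected variables included age, body mass index (BMI), intraoperative blood loss, operative duration, and length of postoperative hospitalization". Section 2.4.2.3 admits a wide spread of operations: "Surgical duration ranging from 0.5 to 4.5 hours". Section 2.4.5 allocates patients from a random-number table in order of enrolment and mentions no stratification.

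**The concern.** Time to first flatus has no pre-treatment value of its own, so any reduction in residual variance has to come from other patient or operation characteristics. Three candidates are already on file. Section 2.2 lists surgical and anaesthetic factors among the causes of postoperative gut dysfunction, which makes it plausible, though the protocol does not say so, that operative duration is related to the endpoint. If any of the three predicts time to flatus, the plain two-sample test leaves that explained variation in its error term and the confidence interval is wider than it need be.

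This is not merely silence that an unseen analysis plan might fill. Section 7 names the tests, and both are unadjusted. What is at stake is precision, and possibly some power, on the one outcome the protocol calls primary.

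**Working it through.** **Inputs from Section 2.4.4.** Control-group mean and SD: "standard deviation of the time to first flatus in the control group was 37.60 ± 4.11" hours. Expected reduction 8.1 h; two-sided alpha 0.05; power 90%; 33 per group, raised to 38 for 15% dropout.

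**Input not in the document.** R2 of age, BMI and operative duration with time to flatus. I assume 0 to 0.3 and show the range.

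**Step 1: the plan's own figure.** The stated formula is n = 2(z_alpha + z_beta)^2 × SD^2 / delta^2. With z-values 1.960 and 1.282, n = 2 × 3.242^2 × 4.11^2 / 8.1^2 = 5.4, so 6 per group. The stated 33 is not reproduced. Solving for the SD that does give 33: 8.1 / (3.242 × sqrt(2/33)) = 10.15 h. The mismatch is a separate problem, but it means that the size of this point has to be shown at both SDs.

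**Step 2: effect of adjustment.** Residual SD = SD × sqrt(1 − R2), so the standard error is multiplied by sqrt(1 − R2). The 95% half-width is t × SD × sqrt(1 − R2) × sqrt(2/33), with t = 1.998 on 64 degrees of freedom unadjusted and t = 2.000 on 61 with three covariates. Power is from the noncentral t distribution.

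| R2 (assumed) | SE factor | Half-width, SD 4.11 h | Half-width, SD 10.15 h | Power for 8.1 h, SD 10.15 h |
|---|---|---|---|---|
| unadjusted | 1.000 | 2.02 h | 4.99 h | 89.1% |
| 0.05 | 0.975 | 1.97 h | 4.87 h | 90.5% |
| 0.1 | 0.949 | 1.92 h | 4.74 h | 92.0% |
| 0.2 | 0.894 | 1.81 h | 4.47 h | 94.6% |
| 0.3 | 0.837 | 1.69 h | 4.18 h | 96.8% |

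At SD 4.11 h the difference is 8.1 / (4.11 × sqrt(2/33)) = 8.0 standard errors, and power exceeds 99.9999% with or without adjustment.

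**Step 3: what the table leaves out.** It ignores the small extra variance from chance covariate differences between arms. For three normally distributed covariates that are unrelated to allocation, and 66 patients, the average variance factor is (66 − 3)/(66 − 3 − 3) = 1.05, about 2.5% on the standard error. The gains shown are therefore slightly generous. At R2 below about 1 − 1/1.05 = 0.05, adjustment gains nothing or costs a little.

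**Step 4: which covariates are safe.** Age and BMI cannot be changed by allocation. Operative duration can be used only if the same is true of it. Section 2.4.3.1 places randomisation after screening and before baseline assessment. Surgical duration is an eligibility criterion in Section 2.4.2.3, which suggests that it was known by then. No section states whether randomisation came before or after surgery. Length of stay follows treatment and is not a candidate.

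**The case against.** The strongest reply is that nothing here is wrong. In a 1:1 randomised trial the unadjusted comparison is unbiased, and its standard error and type I error already allow for chance imbalance. Covariate choice is often left to the analysis plan, and the document gives no evidence that age, BMI or operative duration predicts time to flatus. Most of this stands. It reduces the point to a suggestion about efficiency. It does not remove it, because Section 7 commits to specific tests and the data for a more precise one are already collected.

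Three stronger readings are tempting, and the documents support none of them:

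- **A chance imbalance in operative duration could pass for a treatment effect, so the unadjusted result cannot be trusted.** This is ordinary sampling error, already counted in the test.
- **The trial needs adjustment to reach its power.** On the protocol's own SD of 4.11 h, power is near 100% without it. The rise from 89% to as much as 97% exists only if the SD is near 10.15 h, a value back-calculated from the sample size and stated nowhere.
- **The nine-fold range of permitted operating times shows strong prognostic value.** The ratio 4.5/0.5 compares eligibility limits. It is not observed spread and says nothing about R2.

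Two practical objections also stand. A linear model replaces the Mann-Whitney route as well as the t test, so non-normality has to be handled. And Section 2.4.2.1 puts enrolment between December 2023 and December 2024, so outcomes may already have been compared; the document does not say.

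**Conclusion.** The point holds as a low-priority improvement. The primary comparison is valid but unadjusted on either route, and it forgoes any precision that three collected variables could give. For an assumed R2 of 0 to 0.3, the standard error falls by 0% to 16% at most, equivalent to between no extra patients and 1/(1 − 0.3) = 1.43 times as many. If the stated SD of 4.11 h is right, the whole benefit is a confidence interval up to 0.33 h narrower on each side (2.02 − 1.69). If the SD is nearer 10.15 h, it is up to about 0.8 h on each side (4.99 − 4.18) and up to about 8 percentage points of power.

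The conclusion rests on an R2 that the document does not give and that could be near zero. Including operative duration also rests on its being unaffected by allocation, which the eligibility criteria suggest but no section states.

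**What to change.** In Section 7, name the primary analysis as a linear regression of time to first flatus, in hours, on arm, age and BMI. Add operative duration only if randomisation followed surgery or the surgical team did not know the allocation, and state in Section 2.4.3.1 which of these applied. Report the adjusted mean difference with its 95% confidence interval, using robust or bootstrap standard errors if the residuals are clearly non-normal. Keep the unadjusted t test or Mann-Whitney comparison as a sensitivity analysis. Do not adjust for length of stay.

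The cost is a sentence or two of text, no new data, and two or three degrees of freedom, with little or no gain if the covariates are weakly prognostic. If outcomes have already been compared between arms, the unadjusted test should remain primary and the adjusted analysis be labelled post hoc.

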4.3.2 Laboratory Parameters

Inflammatory markers included C-reactive protein (CRP), serum interleukin-6 (IL-6), serum tumor necrosis factor- α (TNF- α), and the systemic immune-inflammation index [SII, SII = (platelet count \times neutrophil count) / lymphocyte count].

Each parameter was assessed once preoperatively, on the day of surgery prior to treatment, and on postoperative Day 5.

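### Section 7 gives non-normal data a rank-test route for two-group and paired comparisons but not for repeated-measures ANOVA, and does not say which analysis decides a marker measured at several time points

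*Protocol*

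**What the plan says.** Section 7 of the protocol begins with a check: "The Shapiro–Wilk test was employed to assess the normality of continuous variables". Two-group and paired comparisons then depend on the result. Normal data go to t tests; for the rest the rule is "For non-normally distributed data, the Mann–Whitney U test was applied for between-group comparisons, and the Wilcoxon signed-rank test for within-group comparisons".

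Comparisons over several visits get one sentence: "Repeated measures analysis of variance (ANOVA) was applied for comparisons across multiple time points between groups". It carries no normality condition, transformation or rank alternative, and it names no variable. The section closes with a common threshold for everything: "All statistical analyses were two-tailed, and a P value of less than 0.05 was considered statistically significant".

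Section 4.3.2 lists CRP, IL-6, TNF-alpha and SII (platelets times neutrophils, divided by lymphocytes) and fixes their sampling: "Each parameter was assessed once preoperatively, on the day of surgery prior to treatment, and on postoperative Day 5". The first two samples precede acupuncture, so Day 5 is the only marker value that treatment can affect.

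**The concern.** The section applies its normality rule to some between-group comparisons and drops it for another that can use the same data. Three of the markers are concentrations bounded at zero, and SII is a product divided by a count. Variables of this kind are often right-skewed, with a spread that grows with the level. ANOVA on untransformed values pools the error over visits, so a visit with a high level can dominate the error term even if treatment does not affect it.

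Two things are at stake. First, one marker may have two between-group results, a rank test at Day 5 and an ANOVA over time, with no stated order between them. The choice could then be made after both are seen. Second, if the ANOVA is taken as the result, a real Day 5 difference may be missed that the same data would show on the log scale.

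**Working it through.** **1. Figures in the plan.** The protocol gives no SD, effect size or power for any marker, so there is no marker figure to reproduce. Section 2.4.4 gives the evaluable number, 33 per arm, and it is used here as stated. It does not follow from that section's own inputs: 2 × (1.960 + 1.282)² × 4.11² / 8.1² = 2 × 10.51 × 16.89 / 65.61 = 5.4, or 6 per arm. That is a separate matter.

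**2. Assumptions, none from the documents.** Log-normal marker; log-scale SD 0.7 (also 0.5 and 1.0); within-patient correlation 0.5 on the log scale; Day 5 level 40% lower with acupuncture (ratio 0.6); no difference at the two earlier visits. The course over time is varied.

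**3. Why the course matters.** For a log-normal variable, SD = median × exp(s²/2) × √(exp(s²) − 1). At s = 0.7 this is median × 1.278 × 0.795 = 1.016 × median. The control-arm variance at each visit is thus proportional to the squared median. Day 5's share of the summed variance is:
- medians 3:15:8 (preoperative, day of surgery, Day 5): 64 / (9 + 225 + 64) = 21%; the day of surgery takes 225 / 298 = 76%
- flat course: 1/3 = 33%
- medians 3:5:15: 225 / (9 + 25 + 225) = 87%

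The smaller Day 5's share, the more the pooled error is made up of visits that carry no treatment effect. On the log scale every visit has SD 0.7 and the effect is ln 0.6 = −0.511 whatever the course.

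**4. Simulated power**, arm-by-time F test, 33 per arm, ratio 0.6, log-SD 0.7. Ranges for untransformed values run from the Greenhouse–Geisser-corrected to the uncorrected test.

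| Assumed course | ANOVA, untransformed | ANOVA, log |
|---|---|---|
| Day-of-surgery peak (3:15:8) | 23–30% | 87% |
| Flat | 53–55% | 86% |
| Day 5 highest | 84–88% | 86–87% |

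Mann–Whitney at Day 5 has about 81% and does not depend on the course. Hand check: the standard error of the Day 5 log difference is 0.7 × √(2/33) = 0.172, and 0.511 / 0.172 = 2.97. A log-scale two-sample test therefore has power near Φ(2.97 − 1.96) = 84%, and the rank test should fall slightly below that.

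**5. Sensitivity to skew**, peak course 3:15:8. At log-SD 0.5, untransformed ANOVA has 49–60%, log ANOVA 99% and Mann–Whitney 98%. At log-SD 1.0 the figures are 9–13%, 56% and 54%.

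**6. Would both tests arise, and would they differ?** With log-SD 0.5 to 1.0, Shapiro–Wilk rejects normality in about 78–99% of samples of 33, so the section's own rule would usually send such a marker to the rank test. At 3:15:8 and log-SD 0.7, Mann–Whitney at Day 5 and the corrected untransformed ANOVA disagree on significance in 66% of simulated trials. In 62% the rank test is significant and the ANOVA is not.

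**7. Type I error** is about 4–6% in every version.

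**The case against.** The strongest reply is that the section already protects the comparison that matters. Treatment can affect a marker only at Day 5, and for a non-normal marker the plan provides a rank test there, which keeps most of the log-scale power (81% against 86–87%). This stands. A reader might infer that the marker analysis has little chance of detecting an effect; the protocol does not support that, because the low figures apply only if the untransformed ANOVA decides.

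A reader might also take it that the protocol puts the markers into ANOVA on the raw scale. It says neither thing. The sentence names no variable and fits the daily symptom score and the GIQLI equally well. That it covers the markers follows from their three time points, and the untransformed scale from the absence of any stated transformation.

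The largest power gap also needs a day-of-surgery peak. Section 4.3.2 says only that this sample precedes treatment, and the first session is 4–6 hours after surgery, so the sample need not be at a peak or even postoperative. If Day 5 is highest, the gap almost vanishes at log-SD 0.7. This too stands, and it is why the loss is given as a range.

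Finally, transformations are often left to a statistical analysis plan, and one may exist. That answers a complaint about missing detail. It does not answer this point: the protocol itself states a rule for non-normal data and then a method that does not follow it.

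**Conclusion.** The inconsistency is on the page: a normality condition governs the two-group and paired tests and is absent from the repeated-measures ANOVA. For a skewed marker this leaves two between-group analyses with no order of precedence.

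The cost depends on which one is used. If Mann–Whitney at Day 5 decides, little is lost. If untransformed ANOVA decides, power at log-SD 0.7 and ratio 0.6 ranges from 23–30% to 84–88% according to the course, against 86–87% on logs. The log scale was essentially never worse. The skew, the course, the correlation and the effect size are all assumptions. The harm is lost power and an open choice between results, not false positives, and it concerns secondary outcomes: the primary outcome is time to first flatus. The point is worth correcting because the correction is cheap.

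**What to change.** Add two statements to section 7.

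- CRP, IL-6, TNF-alpha and SII are log-transformed for the between-arm analysis, including any repeated-measures analysis.
- One analysis per marker decides. For example: the log Day 5 value compared between arms, adjusted for the log pre-treatment value, and reported as the geometric mean ratio (acupuncture/control) with its 95% CI. State which of the two pre-treatment samples is used. Any other test of that marker is supportive.

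At the assumed correlation of 0.5, adjustment shrinks the standard error by √(1 − 0.25) = 0.866, from 0.172 to 0.149. Then 0.511 / 0.149 = 3.43, and power is near Φ(3.43 − 1.96) = 93% by normal approximation, whatever the course over time.

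The cost is two sentences and no new data. The downside is that results read as ratios rather than differences in the original units. Since section 2.4.2.1 describes recruitment to December 2024 in the past tense, the change should be dated and should say whether marker data had been seen by arm.

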2.1 Study Overview

To investigate the clinical efficacy of abdominal acupuncture in promoting gastrointestinal functional recovery following gynecologic laparoscopic hysterectomy, with the aim of reducing postoperative complications, enhancing postoperative quality of life, and providing a safe, convenient, and effective therapeutic strategy for clinical practice.

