4.3 Efficacy Parameters

4.3.1 Clinical efficacy indices

- **Recovery of gastrointestinal motility** including time to first postoperative passage of flatus (recorded to the exact hour and minute), time to first postoperative bowel movement (recorded precisely), and restoration of bowel sounds.
- **Incidence of postoperative gastrointestinal dysfunction** related complications: including abdominal distension or pain, nausea, vomiting, and diarrhea.

All the above parameters were observed starting on the day of surgery and continued to be

recorded daily until the fifth postoperative day or discharge, whichever came first.

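### Section 7 gives the label significant to any P below 0.05, for the one primary outcome and 13 to 19 further between-arm comparisons alike, so secondary claims have no error control

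*Protocol*

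**What the plan says.** Section 7 ends with one rule for the whole trial: every analysis is two-sided, and "a P value of less than 0.05 was considered statistically significant".

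Section 2.4.4 is clear about the primary outcome: "The primary outcome measure was the time to first postoperative flatus". The sample size there is set at a two-sided 0.05. Section 4.3.1, where the efficacy outcomes are defined, lists flatus time beside first bowel movement and bowel sounds and does not mark it as primary. Sections 4.3.1 to 4.3.3 add complications, inflammatory markers, pain, a daily symptom score and the GIQLI, also unranked.

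Section 2.1 describes the trial as done "with the aim of reducing postoperative complications, enhancing postoperative quality of life". Both of these aims rest on secondary outcomes only.

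For outcomes measured repeatedly, Section 7 names repeated-measures ANOVA for the comparison of groups across time points.

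**The concern.** A protocol may leave ranking of secondary outcomes to the statistical analysis plan. This one has instead fixed a rule, and the rule gives the same label to a powered primary result and to any one of a long list of other comparisons. A report that follows it could state a significant reduction in nausea, a significant fall in IL-6 or a significant gain in GIQLI from whichever comparison happens to fall below 0.05. The 5% applies to each test singly, and a reader of such a report would not see how many chances there were. At stake is what the trial may conclude beyond flatus time, including the two aims named in Section 2.1.

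**Working it through.** **The plan's own figure.** The protocol gives no figure for overall error across secondary outcomes, so there is none to reproduce. Its only error rate is the two-sided 0.05 of Sections 2.4.4 and 7.

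**Step 1: count the between-arm comparisons after treatment, apart from flatus time.**

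| Outcome | Section | Each visit separate | One test per scale |
|---|---|---|---|
| First bowel movement, bowel sounds | 4.3.1 | 2 | 2 |
| Distension or pain, nausea, vomiting, diarrhea | 4.3.1 | 4 | 4 |
| CRP, IL-6, TNF-α, SII at Day 5 | 4.3.2 | 4 | 4 |
| Pain VAS | 4.3.3 | 1 | 1 |
| Symptom score, Days 1 to 5 | 4.3.3 | 5 | 1 |
| GIQLI, two visits after treatment | 4.3.3 | 2 | 1 |
| Sum | | 18 | 13 |
| Length of stay | 4.1 | 1 | 1 |
| Sum with length of stay | | 19 | 14 |

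The VAS time points are worded unclearly and are counted once. Within-group tests and separate ANOVA interaction tests are left out.

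**Step 2: independent tests, no true effect on any of them.** With k tests, the chance of at least one two-sided P<0.05 is 1 − 0.95^k. The chance of at least one such result in favour of acupuncture is 1 − 0.975^k.

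- k = 13: 1 − 0.95^13 = 48.7%; 1 − 0.975^13 = 28.0%
- k = 14: 1 − 0.95^14 = 51.2%; 1 − 0.975^14 = 29.8%
- k = 19: 1 − 0.95^19 = 62.3%; 1 − 0.975^19 = 38.2%

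The expected number of false significant results is 0.05 × 13 = 0.65 to 0.05 × 19 = 0.95.

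**Step 3: correlated tests.** The outcomes are related, so independence is an upper case. The protocol gives no correlations; 0.3 and 0.5 are assumed. Test statistics were simulated as normal with a common correlation (200,000 draws).

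| k | Correlation | Any false difference | False benefit |
|---|---|---|---|
| 13 | 0.3 | 42% | 21% |
| 13 | 0.5 | 33% | 17% |
| 14 | 0.3 | 44% | 22% |
| 14 | 0.5 | 35% | 18% |
| 19 | 0.3 | 53% | 27% |
| 19 | 0.5 | 41% | 21% |

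**Step 4: the lowest case in these tables.** With 13 tests and correlation 0.5, the chance of a false benefit is about 17%. One test alone has 2.5% in that direction, so the ratio is 17 / 2.5, about 7.

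**Step 5: sensitivity to Fisher's exact test.** Section 7 allows it for the four complications, and it is conservative. At 38 per arm its true size is about 1.5% if the incidence is 10% (assumed). With independent tests, the chance of any false difference is then 1 − 0.95^9 × 0.985^4 = 41% for k = 13 and 1 − 0.95^15 × 0.985^4 = 56% for k = 19, against 49% and 62%. This lowers the figures but stays within the range already shown.

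**The case against.** The strongest reply is that the sentence in Section 7 is an ordinary per-test convention. It promises no familywise rate, and ranking of secondary outcomes or an exploratory label may stand in a statistical analysis plan that is not shown. That is right as far as it goes: the mere absence of an adjustment is no error here. What remains is that the protocol states a blanket rule, and a later plan that ranked outcomes or withheld the label from secondary results would have to depart from it.

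The count can also be disputed. Section 7 assigns repeated outcomes to ANOVA, and length of stay is a general parameter in Section 4.1, so 13 is a fair reading and 19 the high end. The outcomes overlap too: the symptom score in Appendix 2 includes flatus, defecation, bowel sounds, distension, nausea, vomiting and diarrhea, and the GIQLI asks about several of the same symptoms. Both points stand and are the reason for a range.

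Two stronger readings are tempting. A reader might infer that a false significant benefit is about as likely as not. The documents do not support that: roughly even odds fit a false difference in either direction, while a false benefit reaches 38% at most in these scenarios, and even odds would need about 27 independent comparisons. A reader might also infer that the primary result is compromised. It is not, because Section 2.4.4 names a single primary outcome tested once at 0.05. The missing label in Section 4.3.1 is an editorial gap and not a contradiction.

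**Conclusion.** The point holds for secondary claims only. With no true effect on any secondary outcome, following Section 7 as written gives about a 33% to 62% chance of at least one false significant difference and about 17% to 38% of at least one false significant benefit. The low ends are 13 tests at correlation 0.5, and the high ends are 19 independent tests. The range rests on assumed correlations and on the count above; a correlation above 0.5 throughout would bring it lower. The primary analysis and its 5% error are untouched. This is a cheap improvement that alters what the trial may claim beyond flatus time. It is not a flaw in the main test.

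**What to change.** Replace the significance sentence in Section 7 with: *Time to first flatus is the only outcome tested for a confirmatory claim, at two-sided 0.05; all other comparisons are exploratory, are reported as estimates with 95% confidence intervals, and are not called statistically significant.* Mark flatus time as primary in Section 4.3.1.

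If the sponsor wants confirmatory secondary claims, it should choose its own short ordered list before seeing results by arm. The protocol gives no basis for a particular order. A complications entry would also need one defined measure, since Section 4.3.1 lists four. Section 2.4.2.1 has enrolment ending in December 2024, so if results by arm have already been seen, the exploratory label is the option that remains.

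The cost is wording in two sections, with no new data or patients. The downside is that some secondary differences lose the label significant.
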